Participants will receive belumosudil treatment in 28-day cycles until clinically significant progression of cGVHD (defined as progression requiring addition of new systemic therapy for cGVHD), histologic recurrence of underlying malignancy, unacceptable toxicity, Investigator decision, participant preference / withdrawal of consent, lost to follow-up, sponsor decision, or death (whichever occurs first).

Participants who experience cGVHD progression as defined by NIH criteria but for whom no new systemic therapy is planned may continue to receive belumosudil and be assessed again at their next cycle. If progression per NIH criteria is not confirmed or no new systemic therapy is planned, participants may continue on belumosudil per investigator discretion until they fulfill one of the criteria requiring discontinuation of study drug.

Under Protocol Amendment 3, all participants (excluding the 20 adolescent participants) that have received at least 6 months of belumosudil treatment or are in long-term follow-up without having a failure-free survival event are expected to end participation in study KD025-213. Participants may continue to participate in study KD025-213 if the Investigative Site is awaiting IRB approval of the KD025-217 rollover study titled: “Extended Treatment and Follow-up of Participants Treated with Belumosudil in Study KD025-208 or Study KD025-213”.

The primary endpoint is the overall response rate (ORR), defined as the proportion of participants achieving a partial response (PR) or a complete response (CR) as defined by the 2014 NIH Consensus Development Project on Clinical Trials in cGVHD ([Appendix B](#)). Response criteria will be assessed after Cycles 1, 2, 3 and 4 and then after every other Cycle thereafter (Day 1 of Cycles 2, 3, 4, 5, 7, 9, 11, etc.) ([Table 6](#)). Following Protocol Amendment 5, in adolescent participants still to be enrolled, response criteria will be assessed after Cycles 1, 2, 4, and 6 and then after every third cycle (Day 1 of cycles 2, 3, 5, 7, 10, 13, etc.). Responses are assessed with respect to baseline.

Analyses of the primary endpoint will be participant to multiplicity adjustment per a Hochberg procedure ([Section 11.2.1](#)).

Secondary endpoints will include assessments to evaluate the clinical meaningfulness of responses. These include duration of response, changes in Lee Symptom Scale Scores, response by organ system and changes in corticosteroid dosage.

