**Table 1: Power for various hypothetic ORRs**

Table 1a: IA Power (1-sided alpha 0.0025)*						
For both arms to be statistically significant						
		Arm 1 ORR (%)				
		40	45	50	55	60
Arm 2 ORR (%)	40	< 1	< 1	< 1	< 1	< 1
	45	-	< 1	1	2	3
	50	-	-	2	6	9
	55	-	-	-	12	22
	60	-	-	-	-	37
For at least one arm to be statistically significant						
		Arm 1 ORR (%)				
		40	45	50	55	60
Arm 2 ORR (%)	40	1	3	10	28	51
	45	-	5	12	29	53
	50	-	-	20	35	57
	55	-	-	-	65	65
	60	-	-	-	-	77
Table 1b: PA Power (1-sided alpha 0.0225)*						
		Arm 1 ORR (%)				
		40	45	50	55	60
Arm 2 ORR (%)	40	20	39	64	84	95
	45	-	52	72	89	97
	50	-	-	83	93	98
	55	-	-	-	97	99
	60	-	-	-	-	100

IA = Interim Analysis; PA = Primary Analysis  
\* Power estimated based upon 10,000 simulations for each cell

The mITT population will be used for tables of demography, baseline characteristics and efficacy.

**Responder:** The responder population is defined as subjects in the mITT population that achieved a partial or complete response at any post-baseline response assessment.

**Nonresponder:** The nonresponder population is defined as anyone in mITT population that is not a responder.

The responder and nonresponder populations will be used for some subgroup analyses.

**Safety:** The safety population is defined as all randomized subjects who receive at least one dose of study medication. In this study, safety population is equivalent to mITT population.

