## **3.8 Efficacy Endpoints and Analyses**

### **3.8.1 Primary Efficacy Endpoint: ORR**

The primary efficacy endpoint is the overall response rate, with response status as assessed by investigators based upon the 2014 NIH Consensus Development Project on Clinical Trials in cGVHD (see Protocol Appendix F: cGVHD Response Assessment).

Response is assessed using individual scores from ten systems (Skin, Eyes, Mouth, Esophagus, Upper GI, Lower GI, Liver, Lungs, Joints and Fascia and Global Severity Rating (GSR)). Response is assessed with respect to the baseline (Cycle 1, Day 1 (C1D1)) cGVHD assessment. The overall response at each assessment time point will be categorized as Complete Response (CR), Partial Response (PR), or Lack of Response (LR), where LR includes the response status of unchanged, mixed, or progression as defined in [Table 2](#).

The ORR is defined as the proportion of subjects with a best response meeting the overall response criteria assessment of CR or PR at any post-baseline response assessment.

If a treated subject is lost to follow up without response assessment, this subject will be counted as a non-responder. Any response on and after new systemic cGVHD treatment will be censored as non-response.

Point estimates, various confidence intervals (Clopper-Pearson (exact) method) listed in Figure 2, and raw and Hochberg adjusted p-values corresponding to the null hypothesis of  $ORR \leq 30\%$  vs alternative hypothesis of  $ORR > 30\%$  by treatment arms will be reported.

The number and percentage of subjects who have a best response of PR and number and percentage of subjects who have a best response of CR will also be reported.

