### 3.8.2.2 Lee Symptom Scale Score (LSS)

Lee cGVHD Symptom Scale (see questionnaire in Protocol Appendix D) will be assessed on Day 1 of Cycles 2-5, then on Day 1 of every other Cycle thereafter and EOT. The questionnaire consists 30 items of 7 domains: skin, eyes and mouth, breathing, eating and digestion, muscles and joints, energy, and mental and emotional. Each question is scored 0, 1, 2, 3 or 4.

A domain score will be calculated for each domain by taking the mean of all items completed if more than 50% were answered and normalizing to a 0 to 100 scale. A summary score will be calculated as average of all nonmissing domain scores if more than 50% of them are nonmissing. A higher score indicated more bothersome symptoms. 7 points difference on the summary score of cGVHD symptom scale was found to be clinically meaningful.

$$\text{Raw Score} = \frac{I_1 + \dots + I_m}{m}, \quad \text{Domain Score} = (\text{Raw Score} / 4) * 100$$

$$\text{Summary Score} = \frac{\text{Domain Score}_1 + \dots + \text{Domain Score}_n}{n}$$

In the above formulas, m is the number of items have nonmissing value in a domain, and n is the number of domains have nonmissing domain scores.

Analyses will include:

- Both score and change-from-baseline values (summary score and domain scores) will be summarized as continuous variables by visit
- Number and percent of subjects with a  $\geq 7$ -point reduction (7-PtR) from baseline (C1D1)
- Number and percent of subjects with a 7-PtR from baseline on 2 consecutive assessments
- Duration of a 7-PtR (DO7-PtR) (defined as time from documentation of the first  $\geq 7$ -point reduction to the first documentation of less than 7-point reduction). If there are multiple episodes, then DO7-PtR will be measured as the sum of DO7-PtR from all episodes.

These analyses will be performed on mITT, responder and nonresponder populations. 7-PtR and DO7-PtR will be censored after new systemic cGVHD treatment.

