### **3.8.2.6 Corticosteroid dose**

Corticosteroid doses will be presented as mg/kg/day prednisone equivalent dose. Descriptive statistics for the mITT population, responder /nonresponder populations and subgroups defined by baseline corticosteroid dose level (upper and lower 50 percentiles) will be provided for:

- Systemic corticosteroid dose over time
- Change and % change from baseline (C1D1) to the greatest corticosteroid dose reduction during KD025 treatment period
- Number and % of subjects who reduced systemic corticosteroid dose during KD025 treatment period

- Number and % of subjects who ever discontinued systemic corticosteroid usage for over 28 days during KD025 treatment period

The above analyses will be censored on or after new systemic cGVHD treatment.

If subjects are not using prednisone as the systemic corticosteroid, then the prednisone dose equivalent will be determined according to following conversion ratios:

1 mg prednisone is equivalent to:

- 4mg Hydrocortisone
- 0.8mg Methylprednisolone
- 0.15mg Dexamethasone
- 1mg Prednisolone
- 0.8mg Triamcinolone

Transient increases in corticosteroid dosing (not exceeding 1mg/kg/day prednisone equivalent, are permitted for the treatment of cGVHD flare, but dose must be reduced back to the pre-randomization dose within 6 weeks. If the dose remains elevated for more than 6 weeks, this will be considered a KD025 treatment failure. More than 2 episodes of cGVHD flare requiring increased corticosteroid therapy in the first 6 months of KD025 treatment will also be considered a KD025 treatment failure.

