### **3.8.2.12 Additional Analyses**

Additional analyses will be presented including:

- ORR and DOR for responses occurring within the first 6 and 12 months of treatment with KD025
- Organ responses according to baseline NIH / severity score
- Landmark FFS with CR/PR at 6 months and at 12 months
- Time to corticosteroid discontinuation

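### Cumulative Lee and corticosteroid measures split by any-time response give responders more time to show the outcome (guarantee-time bias)

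*SAP*

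**What the plan says.** SAP 3.4 fixes the two groups by what happens at any time on study: "The responder population is defined as subjects in the mITT population that achieved a partial or complete response at any post-baseline response assessment", and "The nonresponder population is defined as anyone in mITT population that is not a responder". SAP 3.8.1 adds: "If a treated subject is lost to follow up without response assessment, this subject will be counted as a non-responder".

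SAP 3.8.2.2 (Lee Symptom Scale) then states: "These analyses will be performed on mITT, responder and nonresponder populations". SAP 3.8.2.6 (corticosteroid dose) calls for "Descriptive statistics for the mITT population, responder /nonresponder populations". The table shells in SAP Appendix A repeat both splits.

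The measures reported in these groups are of two kinds:

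- **Cumulative.** For Lee: a reduction of at least 7 points at any time, the same on two consecutive assessments, and its duration summed over episodes. For steroids: greatest dose reduction, any dose reduction, and ever stopping for more than 28 days, all over the treatment period.
- **By visit.** Lee scores and changes from baseline, and steroid dose over time.

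The cumulative measures are censored at new systemic cGVHD therapy. No common time window, landmark or exposure adjustment is specified for the split.

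**The concern.** Response at any assessment can only be recorded while a participant is still being assessed. Those who leave early had little chance to respond and fall into the non-responder group. Those who stay longer had more chances to respond and also more visits at which a 7-point reduction or a steroid reduction could be recorded. Group membership depends on later events, and the two groups have unequal time at risk. Censoring at new systemic therapy does not equalise it.

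The contrast bears on interpretation. Protocol 3.1 says "Secondary endpoints will include assessments to evaluate the clinical meaningfulness of responses", and names Lee scores and corticosteroid dosage among them. Both arms receive belumosudil, so comparing responders with non-responders is a natural way to argue that an NIH response benefits participants. These tables could show such a difference when there is no true link.

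**Working it through.** The documents give no figure for this split, so there is nothing to reproduce. The check is a simulation in which response and a 7-point Lee reduction are independent. Any gap is then an artefact.

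**Mechanism.** With a chance q of a 7-point reduction at each of K assessments, P(at least one) = 1 − (1 − q)^K. The answer depends on K, and K differs between the groups.

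**Check A: 12 assessments.** All rates are assumptions: q = 10% per visit, and exit after each visit at the rate shown. The twelfth assessment on the SAP Lee schedule ("will be assessed on Day 1 of Cycles 2-5, then on Day 1 of every other Cycle thereafter and EOT") is C21D1.

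| Response pattern | Exit per visit (responder / non-responder) | Ever 7-point reduction: responders vs non-responders |
|---|---|---|
| 35%, 20%, 10%, then none | 10% / 10% | 50% vs 47% |
| 35%, 20%, 10%, then none | 5% / 15% | 59% vs 39% |
| All at first visit | 5% / 10% | 58% vs 48% |
| All at first visit | 5% / 20% | 58% vs 35% |
| 15% at every visit | 10% / 10% | 57% vs 34% |
| 25% at every visit | 10% / 10% | 55% vs 27% |
| 20% at every visit | 5% / 20% | 62% vs 24% |

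Implied ORR, for comparison with the 55% assumed in SAP 3.1:

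- Early pattern, equal exit: 0.35 + 0.65 × 0.9 × 0.2 + 0.65 × 0.9 × 0.8 × 0.9 × 0.1 = 51%.
- 15% per visit: 0.15 × (1 − 0.765^12) / (1 − 0.765) = 61%, where 0.765 = 0.85 × 0.9.
- 25% per visit: 0.25 × (1 − 0.675^12) / (1 − 0.675) = 76%, where 0.675 = 0.75 × 0.9.
- 20% per visit, unequal exit: 0.2 × (1 − 0.64^12) / (1 − 0.64) = 55%, where 0.64 = 0.8 × 0.8.

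Over only five assessments (through C7D1) with equal 10% exit, the gap is 37% vs 32% (15% response per visit) or 37% vs 29% (25%).

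**Check B: SAP Lee schedule, calibrated.** ORR 55% and 10% never assessed are taken from SAP 3.1. Assumed: exponential time on treatment with median 9 months, the same for everyone; data cut at 12 months; q = 10%.

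- Responders average 6.6 assessments and non-responders 2.9.
- Ever a 7-point reduction: 48.9% vs 23.1%, or 36.1% for non-responders if those never assessed leave the denominator, as the missing-data rule in SAP 3.14 implies.
- Two consecutive reductions: 5.2% vs 2.1%.
- Varying the median (6, 9, 12 months), the cut (6, 12, 24 months) and q (5%, 10%, 20%): from 20.1% vs 8.8% to 84.8% vs 43.2%.
- A best-value-over-all-visits measure, built like the greatest steroid reduction, from pure noise with SD 10: mean 12.7 vs 9.4 among those assessed.

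Response timing in Check B, among those assessed:

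| Responses possible at | Responders vs non-responders |
|---|---|
| First visit only | 44.5% vs 44.7% |
| First three visits | 46.4% vs 41.3% |
| All visits | 49.1% vs 36.1% |

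**With a landmark.** In Check A, taking response status at the fifth assessment among those still on study, and counting over those five visits, gives 41% vs 41%. This is the value expected with no association: 1 − 0.9^5 = 41%. In Check B, a C7D1 landmark counting later events gives 20.6% vs 20.7%.

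**By-visit summaries.** The proportion with a 7-point reduction at C7D1 in Check B is 10.1% vs 10.1%. Time at risk alone does not inflate them.

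**The case against.** **These are descriptive tables.** SAP 3.2 gives only descriptive statistics for secondary and exploratory endpoints, alpha goes to ORR alone, and no test between responders and non-responders is specified. The protocol's own Lee and steroid definitions (11.7.2) contain no such split. The mITT results are reported alongside, and time to steroid discontinuation is analysed by Kaplan-Meier in mITT. All of this stands, and it limits the point to interpretation.

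**The gap may be small.** If responses come early and both groups leave at the same rate, it is 50% vs 47% or nil. That stands as one end of the range. Equal exit is the doubtful part. Protocol 3.1 and 4.7 end treatment at progression requiring new systemic therapy, so leaving is tied to failure. With all responses at the first visit but non-responders leaving faster, the gap returns (58% vs 35% in Check A).

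A reader might also infer three stronger claims that the documents do not support:

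- **That PROMIS is inflated in the same way.** SAP 3.8.3.1 uses the same split, but its only cumulative count is of reductions of at least 4.7 points on a scale where higher is better. Longer follow-up would add worsening to the responder group. The other PROMIS summaries are by visit.
- **That the SAP already applies a landmark by response status to FFS.** SAP 3.8.2.12 lists "Landmark FFS with CR/PR at 6 months and at 12 months". Elsewhere the SAP uses landmark for a rate at a time point, so this may mean the proportion failure-free and in response then. It is ambiguous and not a settled precedent.
- **That every table split by response is affected.** The by-visit summaries are not inflated by time at risk, although selection by who remains on treatment can still affect them.

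**Conclusion.** The concern holds for the cumulative Lee measures in SAP 3.8.2.2 and the cumulative steroid measures in SAP 3.8.2.6. As specified, these can favour responders without any true association. The direction follows from the definitions whenever responders are observed longer.

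The size cannot be fixed from the documents, because they give neither response timing nor exit rates by response status. With q assumed at 10%, it runs from no gap to 62% vs 24%, so a large advantage is possible but not certain. Any real benefit in responders would add to the artefact, and the planned tables could not separate the two. The primary ORR analysis, the mITT summaries and the by-visit summaries are outside this point.

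**What to change.** For the cumulative measures in SAP 3.8.2.2 and 3.8.2.6 only:

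- Define responder and non-responder by response status at a fixed landmark, for example 6 months (C7D1), among participants still on study then.
- Count the outcomes over the same closed window in both groups, for example baseline to C7D1. An open-ended count after the landmark would let unequal exit back in.
- If the any-time split is kept beside it, label it as not adjusted for time at risk.
- Leave the mITT and by-visit summaries as they are.

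The cost is SAP wording and a few re-programmed tables, with no new data. The downside is that participants who leave before the landmark drop out of this split, though they remain in the mITT summaries, and responses after the landmark do not count towards group membership.

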### **3.8.2.3 Response by organ system**

The best response (CR, PR) for the nine individual organs (Skin, Eyes, Mouth, Esophagus, Upper GI, Lower GI, Liver, Lungs, and Joints and fascia) plus global severity rating will be summarized.

Time to response at the organ level will also be evaluated. Descriptive statistics and plots of cumulative number and % of responders over time (4, 8, 12, 16, 24, 32, 40,  $\geq 48$  weeks) will be provided. Two series of percentages will be presented:

1. with total number of subjects in mITT with involvement of the given organ at baseline as denominator
2. with number of subjects in the responder population with involvement of the given organ at baseline as denominator.

### **3.8.2.4 Time to Response (TTR)**

TTR will be measured as the time from first treatment to the time of first documentation of response. Descriptive statistics and plots of cumulative number and percent of responders over time (4, 8, 12, 16, 24, 32, 40,  $\geq 48$  weeks) will be provided. TTR analyses will only be conducted for the responder population.

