11.7.2 Secondary Efficacy Endpoints

Secondary endpoints are as follows:

- Duration of response (DOR): Assessments of DOR will include:
 - The time from initial response of PR or CR until documented progression from best response of cGVHD, new cGVHD therapy, or death.
 - Time from initial response to start of additional systemic cGVHD therapy or death.
- Changes in the Lee Symptom Scale Score: Analyses will include:
 - Number of participants with a ≥ 7 point reduction.
 - Number of participants with a ≥ 7 point reduction on 2 consecutive assessments.
 - Duration of a ≥ 7 point reduction.
- Response by organ system: The response assessment for the nine individual organs (Skin, Eyes, Mouth, Esophagus, Upper GI, Lower GI, Liver, Lungs, and Joints and fascia).
- Time to response (TTR): defined as the time from the first dose of belumosudil to the first documented cGVHD response.
- Time to next therapy (TTNT): defined as the time from the first dose of belumosudil to the start of additional systemic cGVHD therapy.
- Number and percentage of participants who have a best response of PR and number and percentage of participants who have a best response of CR.
- Change in corticosteroid dose:
 - The prednisone equivalent dose of corticosteroids (mg/kg/day) during the study will be analyzed ([Appendix K](#)).
- Change in calcineurin inhibitor dose.
- Failure-free-survival (FFS): FFS is defined as the absence of cGVHD treatment change, non-relapse mortality and recurrent malignancy ([Section 6.3.5](#)). Median FFS (from first dose of belumosudil) and landmark FFS at 1 year will be analyzed.
- Overall survival (OS): Defined as time from first dose of belumosudil to the date of death due to any cause.
- Changes in cGVHD global severity rating using the Clinician-Reported Global cGVHD Activity Assessment.

- Changes in symptom activity using the cGVHD Activity Assessment Patient Self-Report.

Descriptive statistics will be provided for all secondary endpoints.

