#### **Reporting of Numerical Values**

Continuous data will be described using descriptive statistics: number of observations (n), mean, standard deviation, median, minimum and maximum. Frequencies and percentages will be used for summarizing categorical data. When categorical data are presented, the percent will be suppressed when the count is zero in order to draw attention to the nonzero counts. The denominator for all percentages, unless otherwise specified, will be the number of subjects in the specified analysis population or group.

Means, medians, standard deviations, and confidence intervals will be reported to one decimal place more than the data reported on the case report form (CRF) or by the laboratory/vendor. Minimum and maximum will be reported to the same number of decimal places displayed on the CRF or by the laboratory/vendor. P-values will be reported to 4 decimal places.

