**Table 4: Efficacy TLFs**

T/L/F	Title	Population
Primary Endpoint: ORR		
T	Overall Response Rate*	miITT
T	Overall response rate (ORR) for responses occurring within 6 months of treatment	miITT
T	Overall response rate (ORR) for responses occurring within 12 months of treatment	miITT
T	Landmark ORR at 6 months	miITT
T	Landmark ORR at 12 months	miITT
F	Forest plot of ORRs (1. all subjects in an arm, subgroups within arm; 2. Two arm combined if ORRs of those two arms are similar)	miITT

 In all tables, figures and listing, results will be presented by two treatment arms and overall, unless otherwise specified.

T/L/F	Title	Population
L	Listing of overall response by subject by visit	miITT
Secondary Endpoint: DOR		
T	Descriptive Kaplan-Meier and landmark (12, 20, 24, 32, 36, 48 weeks) statistics for DOR*	Responder
F	Kaplan-Meier plot of DOR*	Responder
L	Listing of all DOR episodes for each subject	Responder
Secondary Endpoint: TTR		
T	Descriptive statistics for cumulative response rate over time (TTR)	Responder
F	Cumulative response rate over time (TTR)	Responder
L	Listing of TTR for each subject	Responder
Secondary Endpoint: LSS score		
T	Descriptive statistics for LSS score for: a) number of subjects with a 7-PtR from baseline; b) number of subjects with 7-PtR on 2 consecutive assessments; c) DO7-PtR (<8, 8-16, 16-24, 24-32, 32-40, 40-48, >48 weeks)	miITT, Responder, Nonresponder
T	Summary of LSS Score (overall and each of seven domains) raw and change from baseline by visit	miITT, Responder, Nonresponder
F	Summary of Lee Symptom Scale Score (overall and each of seven domains) raw and change from baseline by visit	miITT, Responder, Nonresponder
L	Listing of Lee Symptom Scale Score by subject, domain and visit	miITT
Secondary Endpoint: Response by Organ System		
T	Best response by individual organ	miITT
T	Organ responses according to baseline NIH / severity score	miITT
L	Listing of organ score and response assessment by subject and visit	miITT
T	Descriptive statistics for cumulative response rate over time (TTR) by organ	miITT, Responder
F	Cumulative response rate over time (TTR) by organ	miITT, Responder
Secondary Endpoint: Corticosteroid Dose		

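### Overall time to response is shown only among responders, so its cumulative response percentage always ends at 100% and late responders are dropped, not censored

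*SAP*

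**What the plan says.** Protocol 11.7.2 makes TTR a secondary endpoint, "defined as the time from the first dose of belumosudil to the first documented cGVHD response". It does not limit TTR to responders.

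SAP 3.8.2.4 asks for "Descriptive statistics and plots of cumulative number and percent of responders over time" at weeks 4, 8, 12, 16, 24, 32, 40 and 48 or later, and adds that "TTR analyses will only be conducted for the responder population". SAP 3.4 defines that group by outcome: "The responder population is defined as subjects in the mITT population that achieved a partial or complete response at any post-baseline response assessment". SAP 3.14 sets the default: "The denominator for all percentages, unless otherwise specified, will be the number of subjects in the specified analysis population or group". SAP Appendix A, Table 4 lists "Descriptive statistics for cumulative response rate over time (TTR") and a matching figure, both with Responder as the population. No censoring rule is given for TTR.

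The section just before, SAP 3.8.2.3, handles organ-level time to response differently. It gives two series of percentages, the first "with total number of subjects in mITT with involvement of the given organ at baseline as denominator" and the second with responders as denominator.

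**The concern.** An output titled as a response rate should show what share of treated participants had responded by each week. This one is computed in people selected for having responded, so it cannot show that.

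Selection at the data cut adds a second problem. The interim and primary analyses fall about 2 and 6 months after the 126th mITT participant is enrolled. A late enrollee who will respond at week 32 has not been seen to respond at either look if follow-up is still shorter than that. Such a person is left out of the TTR summary, while a quick responder enrolled on the same day is kept. This is right truncation, and it pulls the displayed times toward early response. What is at stake is the reading of a descriptive secondary endpoint.

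**Working it through.** The plan states no TTR figure, so there is none to reproduce.

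**End of the curve.** With R responders among N mITT participants, the responder-only percentage ends at R/R = 100%. The mITT percentage ends at R/N. For the planned 63 per arm:

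| Responders | mITT end (R/63) | Responder-only end |
|---|---|---|
| 19 | 30.2% | 100% |
| 35 | 55.6% | 100% |
| 47 | 74.6% | 100% |

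This needs no assumption.

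**Shape of the curve.** Take the SAP's assumed ORR of 55%, reached by week 48. Assume complete follow-up and exponential response times with a median of 12 weeks, so F(t) = 1 − 2^(−t/12). The responder-only percentage is F(t)/F(48). The mITT percentage is 0.55 × F(t)/F(48).

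| Week | 4 | 8 | 12 | 16 | 24 | 32 | 40 | 48 |
|---|---|---|---|---|---|---|---|---|
| Responder-only % | 22 | 39 | 53 | 64 | 80 | 90 | 96 | 100 |
| mITT % | 12 | 22 | 29 | 35 | 44 | 49 | 53 | 55 |

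The first row is the same for any ORR.

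**Truncation at the data cut.** Inputs from the documents are the cuts at about 2, 6 and 12 months after the 126th mITT participant (SAP 3) and the main-cohort response visits at weeks 4, 8, 12, 16 and then every 8 weeks (Protocol 3.1). The rest is assumed:

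- Accrual is uniform over A = 12 or 24 months. Protocol 3.3 gives about 24 months, but for the enlarged study; the documents do not give it for these 126.
- Latent response times are exponential with mean m = 6, 8, 12 or 20 weeks.
- There is no dropout, and 1 month is 4.348 weeks.

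For visit weeks v_k:

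- p_k = exp(−v_(k−1)/m) − exp(−v_k/m), with v_0 = 0, is the chance that response is first documented at visit k.
- The true mean TTR is Σ p_k v_k.
- With a cut c after the last enrolment, visit k has been reached with probability s_k = (c + A − v_k)/A, held between 0 and 1.
- The mean TTR among observed responders is Σ p_k s_k v_k / Σ p_k s_k.

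Example with m = 20 and A = 12 months at the primary analysis: the true mean is 23.05 weeks and the observed mean 17.83, so it is short by 5.2 weeks. The share responding by week 24 reads 79% against a true 70%; with 24-month accrual it reads 75%.

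Weeks by which mean TTR is short, at 12-month / 24-month accrual:

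| m (weeks) | True mean | Interim | Primary | 12-month |
|---|---|---|---|---|
| 6 | 8.40 | 0.61 / 0.30 | 0.09 / 0.05 | 0.00 / 0.00 |
| 8 | 10.50 | 1.26 / 0.61 | 0.32 / 0.16 | 0.02 / 0.01 |
| 12 | 14.73 | 3.12 / 1.52 | 1.32 / 0.67 | 0.26 / 0.13 |
| 20 | 23.05 | 8.42 / 4.50 | 5.23 / 2.89 | 2.17 / 1.21 |

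The mean is a better guide here than the median, which can only move in whole visits. With m = 12 and 12-month accrual, the share responding by week 8 rises only from about 49% to 50.5% at the primary analysis, yet the median drops from week 12 to week 8.

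**The case against.** Much of the missing information is already planned. SAP 3.8.2.4 asks for cumulative numbers as well as percentages, so a reader who knows the mITT size can rebuild the mITT percentage at each listed week. SAP 3.8.2.12 adds "ORR and DOR for responses occurring within the first 6 and 12 months of treatment with KD025", and Appendix A, Table 4 lists these ORR tables and landmark ORR at 6 and 12 months in mITT, by arm. That stands and lowers the weight of the point. The tables cover only two time points, however, and rebuilt percentages still do not allow for short follow-up.

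The responder restriction is openly stated and answers a fair question: among those who respond, how soon? That also stands, and the summary should be kept. What it does not support is the response-rate title, or having no mITT version when the organ-level section has one.

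A reader might infer that the alpha-bearing analyses are biased. They are not: SAP 3 gives alpha only to ORR, and SAP 3.2 makes every secondary endpoint descriptive. A reader might also infer that an arm with fewer but faster responders could pass for the better one. The primary table reports mITT ORR by arm, and each arm is tested against 30% with no formal comparison between arms. Finally, a reader might take one large truncation figure as established. The documents do not give the inputs for it, and if responses are early the effect at the primary analysis is close to zero.

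**Conclusion.** The point holds as a presentation defect in a descriptive secondary endpoint. The 100% endpoint follows from the SAP's own definitions. The truncation is real in direction, always toward faster response, but its size depends on inputs that the documents lack. Under the stated assumptions, mean TTR is short by about 0.1 to 5.2 weeks at the primary analysis, 0.3 to 8.4 weeks at the interim and 0 to 2.2 weeks at the 12-month analysis. The upper ends need slow response (mean 20 weeks) and 12-month accrual. The ORR test, its alpha and any efficacy claim are unaffected. This is a cheap improvement, not a threat to the trial's conclusions.

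**What to change.** In SAP 3.8.2.4 and Appendix A, Table 4:

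- Add cumulative response by time, by arm, with all mITT participants as the denominator, mirroring the first series in SAP 3.8.2.3.
- Preferably estimate it as cumulative incidence of first response, with new systemic cGVHD therapy and death as competing events and everyone else without a response censored at the last response assessment. This deals with truncation as well as the denominator.
- Keep the responder-only summary and retitle it as time to response among responders.

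The cost is one more table column and curve, a short censoring rule, and lower displayed percentages. The competing-risk version takes somewhat more programming than a simple mITT percentage. No new data are needed.
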